**Study Design Schema [Required]**

Data source          Mass General Brigham ANCA-associated vasculitis cohort
	
Index dates
 
 
• Analysis 1: Date of avacopan prescription or date of non-avacopan, non-glucocorticoid treatment prescription (i.e., immunosuppressive drugs specified in Appendix C)
 
• Analysis 2: Date of avacopan prescription (for both avacopan initiators and non-initiators)
 
• Analysis 3: Date of avacopan initiation
 

Additional details regarding inclusion/exclusion criteria, endpoints, and outcomes are described in Analysis-specific schema
	

[figure not shown]

Index date          Date of avacopan prescription or date of non-avacopan, non-glucocorticoid treatment prescription
	

Inclusion criteria
 
 
• Diagnosed with new or relapsing GPA or MPA on or after December 1, 2021, the first date of avacopan use at Mass General Brigham
 
• At least 18 years old on index date
 
 
Exclusion criteria
 
 
• A diagnosis of EGPA.
 
• GPA/MPA attributed to cocaine/levamisole.
 
• No treatment of GPA/MPA during the baseline or follow-up periods (i.e., not treated for their GPA/MPA).
 
	
Characteristics to be evaluated
 
 
• Demographic features (e.g., age, sex, race/ethnicity)
 
• GPA/MPA features (e.g., BVAS v3, organ involvement, new or relapsing disease)
 
• Comorbidities at index date (e.g., hypertension, hyperlipidemia, Charlson Comorbidity Index)
 
• Healthcare resource utilization up to 12 months prior to index date
 

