Among patients who use avacopan, to describe the outcomes, including disease- and treatment-specific outcomes	
 
• Complete remission at Month 6
 
• Complete remission at Month 12
 
• Proportion who achieve discontinuation of glucocorticoids for treatment of GPA or MPA 1 month before Month 6 and disease remission (based on a BVAS v3 of 0) within 6 months of avacopan initiation, as defined in ADVOCATE
 
• Proportion who achieve sustained remission at Month 12.
 
• Cumulative glucocorticoid exposure
 
• Median daily glucocorticoid dose
 
• Glucocorticoid toxicity
 
• Glucocorticoid Toxicity Index – Metabolic Domain (GTI-MD)
 
• Change in A1c
 
• Change in BMI
 
• Change in lipids
 
• Renal parameters (estimated glomerular filtration rate [eGFR], proteinuria, hematuria)
 
• ANCA titers
 
• Pathology results
 
• Adverse Events
 
• Patient reported outcome measures (RAPID-3, mHAQ, PHQ-8, GAD-7, and PROMIS)
 

Secondary	
To investigate baseline factors associated with glucocorticoid discontinuation and relapse risk in patients who initiate avacopan	Descriptive analysis of baseline demographic and clinical characteristics 
 
• Demographic features (e.g., age, sex, race/ethnicity)
 

	
 
GPA/MPA features (e.g., BVAS v3, organ involvement, new or relapsing disease)
 
Comorbidities at index date (e.g., hypertension, hyperlipidemia, Charlson Comorbidity Index)
 
Healthcare resource utilization up to 12 months prior to index date
 

To evaluate the association of glucocorticoid use patterns with relapse risk in patients who initiate avacopan	
Relapse, defined as a return (after prior improvement) of vasculitis activity on the basis of at least one major BVAS/WG item, at least three minor BVAS v3 items, or one or two minor BVAS v3 items for at least two consecutive clinical visits (ADVOCATE definition). Relapses will be assessed after Month 1.
 
Patients who had an increase in the BVAS v3 of <3 and the absence of major BVAS/WG items define a minor relapse. All other patients are defined as a major relapse. (Miloslavsky et al. 2015)

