To evaluate healthcare resource utilization during follow-up in patients who initiate avacopan	Per patient per month estimates of all-cause and GPA/MPA-related healthcare resource utilization (HCRU) including outpatient visits, hospitalization rates and length of stay, Emergency Room visits
Exploratory	
To evaluate baseline healthcare costs in patients who are and are not prescribed avacopan for GPA/MPA (analysis from MGH only)	Per patient per month costs of all-cause and GPA/MPA-related resource use associated with outpatient visits, hospitalizations, Emergency Room visits
To evaluate baseline healthcare costs in patients who do and those who do not initiate avacopan (analysis from MGH only)	
To evaluate healthcare costs during follow-up in patients who initiate avacopan (analysis from MGH only)	All-cause and GPA/MPA-related costs associated with outpatient visits, hospitalizations, Emergency Room visits
To explore the outcomes, including disease- and treatment-specific outcomes, of patients who use avacopan for greater than 12 months	
Descriptive analysis of demographic and clinical characteristics and outcomes
 
 
Demographic features (e.g., age, sex, race/ethnicity)
 
GPA/MPA features (e.g., BVAS v3, organ involvement, new or relapsing disease)
 
Comorbidities at index date (e.g., hypertension, hyperlipidemia, Charlson Comorbidity Index)
 
Healthcare resource utilization
 

- Glucocorticoid exposure, glucocorticoid toxicity
- Disease activity, renal outcomes, ANCA titer changes
- Change in comorbidities/biomarkers (e.g., BMI, lipids, A1c)
- Healthcare resource utilization (analysis from MGH only)
- Patient reported outcome measures
- Adverse events attributed to avacopan, infection, relapse, mortality

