#### **Follow-up**

Analysis 1: Comparing baseline features among those prescribed and those not prescribed avacopan

Index Date

- Date of avacopan prescription or date of non-avacopan, non-glucocorticoid treatment prescription (Appendix C, immunosuppressive drugs)

Follow-Up Date

- There is no follow-up period, as this analysis is examining baseline factors

Analysis 2: Comparing baseline features among those initiating and those not initiating avacopan after prescription

Index Date

- Date of avacopan prescription (for both avacopan initiators and non-initiators)

Analysis 3: Month 1, 3, 6, and 12 outcomes among patients who initiate avacopan

Index Date

- Date of avacopan initiation

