### Clinical Outcomes

- Date of relapse (any and stratified by major or minor), (for time from initiation to relapse)
- Date of death (for time from initiation to death)
- Date of end of follow-up (for time from initiation to outcomes of interest)
- Date of loss to follow-up (for time from initiation to outcomes of interest)
- Date of adverse event or other event of interest in specific analyses (for time from initiation to adverse event)

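### The exploratory objective on use beyond 12 months sets no time origin; counted from initiation, the only origin given, death is impossible by selection in the first year

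*Protocol*

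**What the plan says.** The exploratory part of the objectives table (Protocol, Research Question and Objective(s)) includes the aim "To explore the outcomes, including disease- and treatment-specific outcomes, of patients who use avacopan for greater than 12 months". Its outcome list ends with "Adverse events attributed to avacopan, infection, relapse, mortality". The same list asks for comorbidities at the index date, but no index date is defined for this objective.

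Elsewhere the protocol gives one origin for outcomes in avacopan users:

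- Study Design Schema: "Analysis 3: Date of avacopan initiation".
- Follow-up, under the heading "Analysis 3: Month 1, 3, 6, and 12 outcomes among patients who initiate avacopan": the index date is "Date of avacopan initiation".
- Clinical Outcomes: "Date of death (for time from initiation to death" and "Date of relapse (any and stratified by major or minor), (for time from initiation to relapse", both measured from initiation.

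For relapse, the objectives table adds "Relapses will be assessed after Month 1". Data Analysis plans cumulative incidence, Kaplan-Meier estimates and Cox models. The text shown mentions no landmark or delayed entry for the long-term users. Hypothesis(es)/Estimation states that outcomes are not tested.

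**The concern.** Membership of the group is decided by a fact known only at Month 12: the patient is alive, still followed and still taking avacopan. If event times start at initiation, the first 12 months of every member enter the denominator although no member could have died in them. A mortality curve would be flat for a year by construction, and a mortality rate would be diluted.

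The same selection acts differently on non-fatal events. A patient who relapses or has an infection in the first year and continues avacopan stays in the group and is counted. One who stops because of the event drops out of the group, and the event goes too. The remaining figures can then be too low.

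No test is needed for this to mislead. The long-term figures would appear in the same report as those for all initiators, and a reader may set them side by side.

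**Working it through.** The protocol gives no figure of its own for this objective, so there is none to reproduce.

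**Input from the document.** The study window in Research Question and Objective(s) runs from December 1, 2021 to May 1, 2024, which is 29.0 months. A user of more than 12 months therefore has a follow-up T from initiation of more than 12 and at most 29 months.

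**Death, lower bound.** The share of time that is death-free by selection is 12/T. A rate counted from initiation is too low by the factor T/(T − 12), relative to the rate in the time when death could be observed.

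- At the longest T: 12/29 = 41%, and 29/(29 − 12) = 29/17 = 1.7.
- Any shorter follow-up makes both larger. At T = 24 they are 50% and 2.0; at T = 18 they are 67% and 3.0.

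So 41% and 1.7-fold are minimum values that need only the window.

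**Death, average case (assumption: start dates uniform over the window).** Mean T among those past Month 12 is (12 + 29)/2 = 20.5 months. The share is 12/20.5 = 59%, and the factor is 20.5/8.5 = 2.4.

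**Check by simulation.** The assumptions, none of them in the document, are uniform start dates, 25% per year stopping avacopan, and constant hazards.

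| Assumed death rate per year | Counted from initiation | Counted from Month 12 |
|---|---|---|
| 3% | 1.2% | 3.0% |
| 5% | 2.0% | 5.0% |
| 10% | 4.0% | 9.9% |

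**Relapse, same assumptions.** The result depends on how often a relapse leads to stopping avacopan.

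| Share of relapses that lead to stopping | Assumed 15% per year, from initiation | Assumed 25% per year, from initiation |
|---|---|---|
| None | 15.0% | 25.0% |
| Half | 10.5% | 17.7% |
| All | 6.0% | 9.7% |

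Counted from Month 12 in patients who have not yet relapsed, the simulated rate is about 15% or 25% in every row. The understatement for relapse thus runs from none to about 2.5-fold (15.0/6.0 = 2.5; 25.0/9.7 = 2.6).

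**The case against.** The strongest reply is that the protocol never says these outcomes are counted from initiation. The objective has no index date, the Analysis 3 heading names only Months 1, 3, 6 and 12, and the objective is not assigned to Analysis 3. It could be read as describing what happens after Month 12. Much of the protocol is redacted and the analysis plan is not shown. This stands in part: the origin is inferred. But the objective refers to an index date, and initiation is the only one offered for outcomes in avacopan users. A section that sets origins for the other analyses leaves this one either inheriting a biased origin or without any.

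Three stronger readings are tempting and are not supported:

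- A reader might infer that relapse, infection and adverse events are also impossible in the first year. They are not. Relapse is assessed after Month 1, and none of these events is said to end treatment.
- A reader might try to size the relapse effect from the 23 relapses and 112 initiators in Study Sample Size. Those are relapses, not stated to be patients. No count of patients who stopped is given, and anyone starting after about May 1, 2023 cannot reach Month 12 by May 1, 2024 whether or not they stopped.
- A reader might infer that the study plans to show longer use to be protective. The objective is exploratory and descriptive, and no outcome comparison of longer with shorter use is planned.

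It is also fair to object that resetting every baseline to Month 12 would discard first-year glucocorticoid exposure and biomarker change, which are legitimate descriptive content. The change should be limited to event outcomes.

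**Conclusion.** The point holds in a limited form. The group is selected by survival and continued use to Month 12, no origin is stated for it, and the only available origin would make the first year death-free by selection. For death the direction is certain if that origin is used. The understatement is then at least 1.7-fold, which rests only on the 29-month window, and about 2.4-fold if starts are uniform, which is an assumption.

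For relapse, infection and adverse events the problem is selection of patients who stayed on treatment, not immortal time. Its size is unknown and may be zero. Because the objective is exploratory, descriptive and untested, this should be corrected but does not threaten the primary objectives.

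**What to change.** For the event outcomes of this objective (death, relapse, infection, adverse events), state a Month 12 landmark, or delayed entry at Month 12, in patients alive and on avacopan then. Count only later events and person-time. For time to first relapse, use those not yet relapsed at Month 12 and give the number who had relapsed earlier.

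Keep the initiation baseline for descriptive changes (BMI, lipids, A1c, ANCA titers) and for cumulative glucocorticoid exposure.

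Beside these results, report how many initiators could have reached Month 12 by the cut-off, how many did so on avacopan, and why the others stopped.

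The cost is a short addition to the text and fewer events shown for the long-term group. The new origin needs no new data.

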### **Hypothesis(es)/Estimation**

This study is primarily descriptive in nature. Hypothesis testing will be used to compare baseline characteristics but not outcomes.

### **Study Design/Type**

This is a retrospective cohort study (chart review)

### **Study Population or Data Resource**

This study will be conducted at Mass General Brigham, a large healthcare system in eastern Massachusetts and New Hampshire, United States. It includes 2 tertiary care hospitals (Massachusetts General Hospital and Brigham and Women's Hospital) and 12 community hospitals, along with all of the associated primary care and specialty outpatient clinics. Data will be collected from December 2020 (12 months prior to first avacopan prescription at MGB) through April 2024 (12 months of follow-up for patients identified up to 6 months after study launch). Data will be collected from the MGB electronic data warehouse (EDW), research patient data registry (RPDR), and by manual chart review of the electronic health record. The study may also be expanded to include the Cleveland Clinic Foundation's Center for Vasculitis Care and Research.

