### Proper Version Numbering and Dating

VERSIONING:

Protocol Version	Date of Protocol	Page Header Date
Original Protocol, Version 1.0	February 19, 2024	February 19, 2024

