### **Research Question and Objective(s)**

This study aims to describe the demographic and disease-specific characteristics associated with avacopan prescription and initiation and the outcomes observed among patients who initiate avacopan in a real-world setting between December 1, 2021 and May 1, 2024. Our research questions, study objectives, and endpoints are as follows:

- What are the demographics and disease-specific features of patients who are and are not prescribed avacopan for GPA/MPA?
- What are the demographics and disease-specific features of patients who do and do not initiate avacopan after prescription?
- What are the outcomes, including disease-specific (e.g., disease activity, renal function) and treatment-specific (e.g., glucocorticoid toxicity, infection), among patients who initiate avacopan?

Objectives	Endpoints
------------	-----------

Primary	
To describe the demographics and disease-specific features of patients who are and are not prescribed avacopan for GPA/MPA	Descriptive analysis of baseline demographic and clinical characteristics
Among people prescribed avacopan, to describe the demographics and disease-specific features of patients who do and those who do not initiate avacopan	
 
• Demographic features (e.g., age, sex, race/ethnicity)
 
• GPA/MPA features (e.g., BVAS v3, organ involvement, new or relapsing disease)
 
• Comorbidities at index date (e.g., hypertension, hyperlipidemia, Charlson Comorbidity Index)
 
• Healthcare resource utilization up to 12 months prior to index date
 

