## Follow-Up Dates (vary by analysis/outcome)

### Treatment Outcomes

- Date of avacopan discontinuation (for time from initiation to discontinuation)
- Date of glucocorticoid discontinuation and usage patterns, including dosage changes (for time from initiation to discontinuation)
- 6 months after avacopan initiation (for primary outcomes at Month 6)
- 12 months after avacopan initiation (for primary outcomes at Month 12)

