### **Study Sample Size**

- There are 133 patients identified through January 2024 from within the Mass General Brigham system who have been prescribed avacopan and 112 have initiated avacopan. Additionally, since December 1, 2021, there are 60 patients diagnosed with GPA/MPA in the MGB system who were not prescribed avacopan. Among those who have initiated avacopan, there have been 23 relapses. Glucocorticoid exposure has varied but the majority of patients have discontinued glucocorticoids within 2 months of avacopan initiation. There are only 2 patients in this cohort with missing status regarding avacopan initiation.

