### **Data Analysis**

- The primary and secondary outcomes will be analyzed using a descriptive approach. Summary statistics for continuous variables, including the number of patients, mean, standard deviation (SD), median, Q1, Q3, minimum and

maximum, will be calculated after excluding missing/unknown values. For categorical variables, the frequency and percentage will be provided, and a category of “missing/unknown” will be included. Cumulative incidence will be used to describe the occurrence of key outcomes, including glucocorticoid toxicities, infections, and relapse. Given the variable follow-up time, healthcare resource utilization (HCRU) and costs will be presented as per patient per month (PPPM) metrics. Time to event outcomes (e.g., time to discontinuation of glucocorticoids) will be calculated using Kaplan-Meier analysis and median follow-up time (interquartile range [IQR]) will be reported.

- Among avacopan users, we will consider analyses evaluating time to events (e.g., glucocorticoid discontinuation, relapse) with adjustment for covariates. We will consider Cox proportional hazard regression models or other methods for time to event analyses and incorporate covariates, considering the number of observed outcomes. Restricted mean survival time will be used to describe time free from glucocorticoid exposure during follow-up.
- Among avacopan users, exploratory analysis of the association of glucocorticoid exposure with the risk of relapse will be assessed using an emulated target trial framework with a clone, censor, weighting approach. Cluster analysis will be used to explore patterns of glucocorticoid prescribing for patients using avacopan. Cox proportional hazards models will be used to evaluate factors associated with the risk of relapse and factors associated with glucocorticoid discontinuation.

CCI

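### The April 2024 end of data and its 12-month follow-up rationale do not fit a cohort counted through January 2024, and no rule limits the Month 6 and Month 12 primary proportions to patients who could reach those months

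*Protocol*

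**What the plan says.** All places are in the Protocol; unless noted, they are subsections of section 4, Abstract.

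- **Data window.** Study Population or Data Resource: "Data will be collected from December 2020 (12 months prior to first avacopan prescription at MGB) through April 2024". The reason given for the end date stands in the same sentence: "through April 2024 (12 months of follow-up for patients identified up to 6 months after study launch"). No launch date is stated.
- **Study period.** Research Question and Objective(s) gives a slightly different end: "real-world setting between December 1, 2021 and May 1, 2024".
- **Cohort to date.** Study Sample Size, and likewise Study Feasibility and Futility Considerations: "There are 133 patients identified through January 2024", of whom 112 have initiated avacopan.
- **Protocol date.** Proper Version Numbering and Dating (front matter) dates Version 1.0 "February 19, 2024".
- **Outcome timing.** Under Follow-Up Dates, Treatment Outcomes: "12 months after avacopan initiation (for primary outcomes at Month 12"), with a matching entry for Month 6. Both primary outcomes of Analysis 3 are proportions at these fixed months.
- **Eligibility.** Summary of GPA/MPA Eligibility Criteria admits to Analysis 3 adults with new or relapsing disease who initiated avacopan. There is no latest start date and no minimum potential follow-up.
- **Summary rule.** Data Analysis: "For categorical variables, the frequency and percentage will be provided", together with a missing/unknown category. For continuous variables, missing and unknown values are excluded instead.

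**The concern.** The sentence that justifies the end of data collection cannot be squared with the protocol's own dates and cohort count. Part of the counted cohort has no Month 12, and a smaller part no Month 6, because of calendar date alone.

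Sustained remission at Month 12 is one of the study's two headline proportions. If patients who have not yet had time to reach Month 12 stay in its base, the displayed percentage falls for a reason unrelated to treatment. If they are simply dropped as missing, a different bias can arise (step 5 of the working). Either way, the number of patients who support the Month 12 result is smaller than 112, and the protocol does not say how much smaller.

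**Working it through.** **1. The plan's own end date.** The stated rule is: end of data = launch + 6 months of identification + 12 months of follow-up.

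- Backwards: April 2024 − 12 months = April 2023 (end of identification); − 6 months = October 2022 (launch).
- Forwards, taking the protocol date as launch (an assumption, since none is given): February 2024 + 18 months = August 2025.
- The cohort count runs to January 2024, about 9 months past the implied end of identification. The protocol date is about 16 months past the implied launch.

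So April 2024 can be reproduced only with a launch near October 2022, which does not fit the period over which patients were counted.

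**2. Latest useful start dates.**

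- Month 12: end of April 2024 − 12 months = end of April 2023. With the May 1, 2024 end date it is May 1, 2023.
- Month 6: end of April 2024 − 6 months = end of October 2023.
- A patient who started in January 2024 has about 3 to 4 months of data.

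**3. How many of the 112 can reach each month.** The documents give no start dates, so accrual is assumed. Starts are spread over December 2021 to January 2024, which is 26 calendar months. Of these, 17 (to April 2023) allow a Month 12 and 23 (to October 2023) allow a Month 6. The share who started by month t is (t/26)^k, with k = 0.5 for front-loaded, 1 for uniform and 2 for rising uptake.

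| Accrual | Can reach Month 12 | Can reach Month 6 |
|---|---|---|
| k = 0.5 | 112 × 0.809 = 91 | 112 × 0.941 = 105 |
| k = 1 | 112 × 0.654 = 73 | 112 × 0.885 = 99 |
| k = 2 | 112 × 0.428 = 48 | 112 × 0.783 = 88 |

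Counting in days, and moving the end of data between April 1 and May 1, 2024 and the last identification between January 1 and January 31, 2024, the uniform case leaves about 69 to 76 able to reach Month 12.

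**4. Effect on the displayed percentage.** As an illustration, take a true Month 12 proportion of 66%, the phase 3 figure in Study Background and Rationale. If all 112 form the base, the display is 0.66 × the share who can reach Month 12:

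- k = 0.5: 0.66 × 0.809 = 53%
- k = 1: 0.66 × 0.654 = 43%
- k = 2: 0.66 × 0.428 = 28%

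Precision among those who can be observed, from 1.96 × √(0.66 × 0.34 / n): 9.7 points for n = 91, 10.9 for n = 73 and 13.4 for n = 48. With n = 112 it would be 8.8.

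**5. Why dropping missing values is not enough.** Sustained remission requires remission at Month 6. A patient who started in July 2023 and was not in remission at Month 6 (January 2024) is already a known failure. A similar patient in remission at Month 6 is unknown at the cut-off, because Month 12 falls in July 2024. Excluding unknowns would keep the first and lose the second. Selection has to be by start date, whatever outcome has been seen.

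**The case against.** Much can be said for the plan.

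- **No denominator is named.** Analysis 3 also covers Month 1 and Month 3 outcomes and time-to-event analyses, in which recent starters belong. A reader might infer that the protocol computes the Month 12 proportion on patients who cannot have one. It does not say so, and an SAP or the redacted text may restrict the base. This stands: dilution is what follows by default from the stated rule, not a stated intention.
- **Unknown is not failure.** A reader might infer that unobserved patients are counted as not in remission. The text gives them their own category, so a careful reader could recompute the percentage among observed patients. This stands too: the effect is a lower displayed percentage, not misclassification.
- **The 12 months is promised to a subset.** The sentence covers patients identified within 6 months of launch, not every initiator, and is internally consistent if launch was near October 2022. This stands. What fails is the fit between that subset and the cohort counted.
- **No comparison with 66% is planned.** The figure is background, and Hypothesis(es)/Estimation rules out testing of outcomes. The number serves here only to show scale.
- **Unequal follow-up is acknowledged.** Data Analysis uses per-patient-per-month metrics for utilization and costs and Kaplan-Meier for time-to-event outcomes. These provisions do not reach the two fixed-month proportions.

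An SAP could define a denominator. It could not make the follow-up rationale agree with the dates or create data after the cut-off.

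**Conclusion.** The point holds as a conflict of dates with a consequence for the primary proportions. The end of data, its rationale, the protocol date and the identification period do not agree. Initiators after about April 2023 cannot contribute a Month 12, nor those after about October 2023 a Month 6, and nothing shown keeps them out of the base.

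The cut-off dates are certain, because they follow from stated dates. The size is not: 48 to 91 of 112 able to reach Month 12, and a display of 28% to 53% for a true 66%, depend on assumed accrual. The display figures further assume that all 112 form the base. The documents do not support saying that the Month 12 result will be biased by a known amount.

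**What to change.** First, correct or delete the 12-month follow-up statement, state the launch date, and reconcile the dates in Proper Version Numbering and Dating, Study Feasibility and Futility Considerations, Research Question and Objective(s), Study Population or Data Resource, and Study Sample Size.

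Then choose one of two routes:

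- **Keep the cut-off.** Restrict the Month 6 and Month 12 proportions to initiators who started at least 6 or 12 months before it, regardless of observed outcome. State the expected n for each month, and show truly missing assessments separately from patients who had not had time to reach the month. The cost is wording and a date filter, with a smaller n and a wider interval at Month 12.
- **Move the cut-off** to 12 months after the last included initiation, which is January 2025 if the last is in January 2024. The cost is a later chart pull.

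How deaths before Month 6 or Month 12 count is a separate choice of estimand that can be left to the SAP.
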